12.2 Analysis sets

The following analysis sets will be defined for the statistical analysis of this study:

Safety evaluation sets

The Safety evaluation set for the unilateral treatment period (SES-UP) includes all subjects who received NT 201 or placebo during the unilateral treatment period.

The Safety evaluation set for the bilateral treatment period (SES-BP) includes all subjects who received NT 201 during the bilateral treatment period.

Full analysis sets

The Full analysis set for the unilateral treatment period (FAS-UP) is the subset of subjects in the SES-UP for whom at least one score of tremor amplitude at wrist level (injected UL) at the study baseline (V2) and at least at one post-baseline score (V3 to V8) during the unilateral treatment period are available.

The Full analysis set for the bilateral treatment period (FAS BP) is the subset of subjects in the SES-BP for whom at least one score of tremor amplitude at wrist level at the Cycle 2 baseline visit (V8) and at least at one post-baseline score (V9 to V11) of both arms during the bilateral treatment period are available.

Per protocol set

The Per protocol set (PPS) is the subset of subjects in the FAS-UP without major protocol deviations. Major protocol deviations will be defined during the blinded data review meeting.

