2.2.1.1 Primary Efficacy Endpoint

Change from study baseline to Week 6 (V4) in maximum tremor amplitude measurement (root mean square (RMS) deg] at wrist level during the unilateral treatment period.

The primary endpoint is based on angular tremor amplitude values recorded by the kinematic sensor for the motor-dominant UL during four tasks repeated in three assessments rounds at both study baseline (defined in Section 4) and Week 6 (V4). The task with the maximum tremor

¹ health state = pattern of scores over the five dimensions, e.g., 13333 for a subject indicating slight problems in mobility and severe problems on the other four dimensions.

amplitude at study baseline is selected. For the computation of the primary efficacy endpoint and further details on statistical analysis see Section 4.1.1.

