2.4 Other Data

- Important protocol deviations (PDs), PDs⁶ and other events related to COVID-19 pandemic
- Reasons for exclusion of subjects from analysis sets

3 Analysis Sets

The following analysis sets are defined for the statistical analysis of this study:

Safety evaluation sets

The Safety evaluation set for the unilateral treatment period (SES-UP) includes all subjects who received NT 201 or placebo during the unilateral treatment period.

The Safety evaluation set for the bilateral treatment period (SES-BP) includes all subjects who received NT 201 during the bilateral treatment period.

Full analysis sets

The Full analysis set for the unilateral treatment period (FAS-UP) is the subset of subjects in the SES-UP for whom at least one score of tremor amplitude at wrist level (injected motor-dominant UL) at study baseline and at least at one post-baseline score (V3 to V8) during the unilateral treatment period are available.

For definition of study baseline see Section 4.

The Full analysis set for the bilateral treatment period (FAS-BP) is the subset of subjects in the SES-BP for whom at least one score of tremor amplitude at wrist level at Cycle 2 baseline visit and at least at one post-baseline score (V9 to V11) of both arms during the bilateral treatment period are available.

For definition of study baseline see Section 4.

Per protocol set

The Per protocol set (PPS) is the subset of subjects in the FAS-UP without major PDs. Major PDs will be defined during the blinded data review meeting.

In any analyses on randomized subjects, the FAS-UP, FAS-BP, and the PPS, subjects will be included according to the randomized treatment group. In any analyses on the SES-UP and SES-BP, subjects will be included according to the actual treatment in Cycle 1.

4 Statistical Analyses

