4.5.3 Other Safety Endpoints

- Exposure to study treatment will be analyzed as follows for both treatment periods:
 - For injected volume, descriptive statistics for metric variables will be provided for by injected muscle, muscle group (total injected volume for forearm/wrist muscles, elbow muscles, shoulder muscles), and total injected UL. The number of subjects injected in respective muscle / in at least one muscle of respective muscle group (M) will be displayed as well.
 - For Cycle 1, the analysis will be performed for the injected UL, irrespective of whether the motor dominant UL (acc. to CSP) or the non-dominant UL was treated.
 - For Cycle 2, the analysis will be performed separately by motor dominant and non-dominant UL, and in total for both injected ULs, but only for muscle group and total UL (i.e., total injected volume over both ULs will not be provided separately by muscle). In case, deviating from CSP, not all subjects were treated in both ULs, the analyses will be performed on the subset of subjects treated at the respective UL / both UL(s), as applicable, in Cycle 2. and an explanation (including Subject ID, treatment group, untreated UL [motor dominant or non-dominant] of affected subjects) will be provided in a footnote.

For both cycles, only data with injected volume larger than 0 ml will be included.

- Number of injection points by muscle [including 0 to account for non-injected muscles for treated UL(s)], by muscle, muscle group (sum of injection points over forearm/wrist muscles / elbow muscles / shoulder muscles) and for total injected UL (total sum of injection points of injected UL).
 - For Cycle 1, the analysis will be performed for the injected UL, irrespective of whether the motor dominant UL (acc. to CSP) or the non-dominant UL was treated.
 - For Cycle 2, the analysis will be performed separately by motor dominant and non-dominant UL. In case, deviating from CSP, not all subjects in SES-BP were treated at both ULs, the analyses will be performed on the subset of subjects treated at the respective UL and an explanation (including Subject ID, treatment group, untreated UL [motor dominant or non-dominant] of affected subjects) will be provided in a footnote.
- Adverse events
 - The following summary tables for Section 14.3 of the CSR will be created for total observation period, Cycle 1 and Cycle 2 (if not stated otherwise below):

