References to the study baseline and the Cycle 2 baseline definition in Section 4 were inserted. These changes were made to ensure consistency of definitions of FAS-UP and FAS-BP with definition of efficacy endpoints specified as changes from at study baseline or changes from Cycle 2 baseline as defined in Section 4 and to avoid unnecessary removal of subjects from these two analysis sets. E.g., the change of the FAS-UP definition implies that a subject who does not have any scores of tremor amplitude at wrist level at study baseline visit (V2) and would thus be removed from the FAS-UP according to the FAS-UP definition in the CSP, will actually be included in the FAS-UP if he/she has at least one score of tremor amplitude at wrist level at screening visit (V1).
- For consistency, “injected UL” was changed to “injected motor-dominant UL” in the definition of the FAS-UP. This is in accordance with the specification in CSP Section 8.1.1 that the motor-dominant UL is to be injected in the unilateral treatment period (Cycle 1), the specification in CSP Section 9.1.1.2.1 that angular tremor amplitude (for evaluation of the primary efficacy endpoint and some other efficacy endpoints) is to be performed “for the injected UL(s), i.e., the motor-dominant UL in the unilateral and both ULs in the bilateral treatment period” and the specification of the unilateral key secondary efficacy endpoint in Section 12.3.1.2.1 (“Change from study baseline to Week 6 in TETRAS Performance dominant UL Score [...] in the unilateral treatment period as assessed by the investigator.”).

Sections 4.1.1.2 & 4.1.2.1:

- For sake of preciseness, “among all treated subjects” was added after “In case more than 10% missingness on the primary efficacy endpoint occurs in either treatment group” in the specification of the condition when sensitivity analysis no 4 (based on multiple imputation) needs to be performed for the primary efficacy endpoint (Section 4.1.1.2).
- Likewise, “among all treated subjects” was added after “in case of more than 10% missingness on the respective key secondary endpoint” regarding to need to perform respective sensitivity analysis for key secondary endpoints (Section 4.1.2.1).

7 References

[1]

[REDACTED]

[2] Elble RJ. The Essential Tremor Rating Assessment Scale. Journal of Neurology & Neuromedicine. 2016;1(4):34-8.

[3]

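### Read literally, the SAP's FAS-UP definition drops a treated subject injected in the non-dominant arm from the main Cycle 1 efficacy analyses, even when the data are complete

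*SAP*

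**What the plan says.** Protocol Section 12.2 defines FAS-UP as the treated subjects with "at least one score of tremor amplitude at wrist level (injected UL) at the study baseline (V2") and at least one score afterwards. SAP Section 3 changes the condition to "for whom at least one score of tremor amplitude at wrist level (injected motor-dominant UL) at study baseline". SAP Section 6 declares the change: "For consistency, “injected UL” was changed to “injected motor-dominant UL” in the definition of the FAS-UP". It gives this reason: "This is in accordance with the specification in CSP Section 8.1.1 that the motor-dominant UL is to be injected".

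The same SAP Section 3 states that in FAS-UP and the PPS "subjects will be included according to the randomized treatment group", and it makes the PPS a subset of FAS-UP. SAP Section 4.1 makes FAS-UP (observed cases) the default set for Cycle 1 efficacy, and SAP Section 4.1.1.1 runs the confirmatory analysis on it.

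The primary endpoint itself does not depend on which arm was injected. SAP Section 2.2.1.1 bases it on amplitudes "recorded by the kinematic sensor for the motor-dominant UL during four tasks", and Table 5 of the protocol schedules Cycle 1 TremorTek recordings on the dominant arm.

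The SAP allows for wrong-arm injection elsewhere. In Section 4.5.3, Cycle 1 exposure and grip strength are analysed for the treated limb "irrespective of whether the motor dominant UL (acc. to CSP) or the non-dominant UL was treated". Section 4.6.1 treats injection guidance the same way.

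**The concern.** A full analysis set is meant to keep randomised, treated subjects whatever went wrong with the treatment. Whether the correct arm was injected is a matter of protocol adherence, and the place to remove such a deviation is the PPS. Here the condition sits in the full set. If it is applied as written, two things follow.

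- A subject whose primary endpoint can be derived is left out of the confirmatory analysis because of how the treatment was given. SAP Section 4.1.2.1 records that both key secondary endpoints were complete for all treated subjects, so complete key secondary data would be set aside too.
- Because the PPS is nested in FAS-UP, comparing the two (sensitivity analysis no. 1) cannot show what this deviation does to the result.

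The stated reason, consistency with the planned procedure, explains which arm should be injected. It does not explain why a subject treated otherwise should leave the full set. The entry just before it in Section 6 widens the baseline rule so that subjects are not removed needlessly, and the arm wording pulls the other way.

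**Working it through.** **Step 1. Which wording excludes whom.** Take a subject randomised and injected in the non-dominant arm, and apply each wording.

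| | A: dominant arm measured, as scheduled | B: injected non-dominant arm measured |
|---|---|---|
| Protocol 12.2, literal | out (no score for the injected arm) | in |
| SAP 3, literal | out | out |
| SAP 3, read as naming the intended arm | in | out (no motor-dominant score) |
| Primary endpoint (SAP 2.2.1.1) | derivable | missing; SAP 4.1 only lists such values |
| Key secondary TETRAS data | complete (SAP 4.1.2.1) | complete (SAP 4.1.2.1) |

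Case A is the one that matters for the primary analysis. There the literal protocol and the literal SAP agree in excluding the subject. The SAP edit changes membership only in case B, where the primary endpoint is missing in any event.

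**Step 2. Which analyses are affected.** The primary analysis, the key and other secondary Cycle 1 analyses and the PPS analyses all rest on FAS-UP or a subset of it. The exception is sensitivity analysis no. 4 (SAP 4.1.1.2). It uses all subjects treated in Cycle 1, runs only if more than 10% of primary endpoint values are missing in either group, and is interpreted descriptively.

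**Step 3. The plan's own figure.** Inputs from protocol Section 12.1 and SAP Section 5: effect 1 SD, two-sided 5%, 2:1 allocation, 90% power, 51 analysable subjects, about 75 randomised. Protocol Section 7.1 gives about 50 NT 201 and 25 placebo. For a two-sample t-test the noncentrality is d / √(1/n₁ + 1/n₂) with n₁ + n₂ − 2 degrees of freedom. Power is 0.892 at 32 + 16 = 48 and 0.910 at 34 + 17 = 51, so 51 is reproduced. The normal approximation gives 48.

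**Step 4. Size per subject.** One subject is 1/75 = 1.3% of the trial, 1/50 = 2% of NT 201, or 1/25 = 4% of placebo. The number of wrong-arm cases is not given; I assume 1 to 5. I also assume that an NT 201 subject injected in the wrong arm has no effect in the dominant arm. With k such subjects retained, the effect is 1 × (50 − k)/50 SD:

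- k = 1: 49/50 = 0.98 SD
- k = 5: 45/50 = 0.90 SD

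With them dropped it stays at 1.00 SD, so dropping them raises the estimate by k/50, or 0.02 to 0.10 SD. Dropping placebo subjects is neutral in expectation.

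**Step 5. Power at 1 SD.** With 50 + 25 it is 0.981.

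| | 1 subject | 5 subjects |
|---|---|---|
| Removed from NT 201 | 0.980 | 0.977 |
| Removed from placebo | 0.978 | 0.961 |
| Retained in NT 201 without effect | 0.977 | 0.952 |

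Power is not the issue either way at the planned effect.

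**The case against.** The strongest reply is that the parenthesis only says which arm's score counts. Protocol Section 9.1.1.2.1 equates the injected limb in Cycle 1 with the motor-dominant one, and SAP Section 6 cites that passage in support of the wording. The neighbouring Section 6 entry does change membership, and it says so with an example; the arm entry claims no such consequence. On this reading a case A subject stays in. It is a fair reading, but it is not the only one, and the two readings give different confirmatory populations.

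A reader might infer that the SAP edit by itself causes the loss. The documents do not support that: in case A the protocol wording already has the same literal effect, and in case B the edit removes a subject whose primary endpoint could not be derived anyway. A reader might also infer that every Cycle 1 efficacy analysis loses these subjects. That is too broad, because sensitivity analysis no. 4, if triggered, keeps them.

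It also counts against a heavier finding that injection was double-blind (protocol Section 8.5), so a wrong-arm error has no evident link to allocation. Important deviations and exclusions were settled at the blinded review of 17Jan2024 (SAP Section 4.6.2), and exclusions will be tabulated and listed. These steps make an exclusion visible but do not remove the literal rule. The documents do not show how wrong-arm injection was classed.

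**Conclusion.** The point holds in a limited form. As literally written, FAS-UP membership depends on correct administration, and a randomised, treated subject injected in the non-dominant arm would leave the full set and the PPS even with complete motor-dominant and TETRAS data. The documents do not show that anyone was injected in the wrong arm. It would go too far to conclude that the reported estimate is biased or that the confirmatory analysis as a whole is no longer as-randomised, since all subjects who remain are analysed in their randomised group.

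The size is about 0.02 SD per affected NT 201 subject, and 0.02 to 0.10 SD for one to five, against a planned 1 SD. This rests on the assumed number of cases, on no dominant-arm effect in those subjects, and on about 50 subjects in the NT 201 group. The effect on power is negligible at the planned effect. This is a cheap improvement of low severity.

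**What to change.** In SAP Section 3 and in the matching Section 6 entry, replace *(injected motor-dominant UL)* with *(motor-dominant UL, irrespective of which UL was injected)*. State that these subjects are analysed in FAS-UP by randomised group. Class wrong-arm injection as a major protocol deviation, so that sensitivity analysis no. 1 on the PPS shows the result without them.

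The cost is one phrase and one deviation class. The sponsor can check the blinded review records to see whether anyone is affected. If nobody is, nothing changes. If someone is, the estimate is slightly diluted, and retaining such NT 201 subjects costs a little more power than dropping them (0.952 against 0.977 for five). The edit does not bring back a subject with no motor-dominant wrist recording (case B), whose primary endpoint stays missing.

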4.1 Efficacy Analyses

If not otherwise specified, efficacy analyses

- for Cycle 1 will be performed on observed cases (OC) in the FAS-UP and by treatment group
- for Cycle 2 will be performed on FAS-BP (OC), by treatment group and in total. However, changes from study baseline (as defined at beginning of Section 4) in efficacy endpoints will generally only be analyzed by treatment group, not in total. "In total" means a pooled analysis of data from both treatment groups. The label "Total" will be used in respective tables.

In case angular tremor amplitude assessments of Cycle 1 are erroneously performed on non-dominant arm, values will only be listed. In the bilateral treatment period, it will be distinguished between:

- *Category A*: endpoints that are

- general (i.e., TETRAS ADL scores, TETRAS Performance subscale scores, GICS scores, QUEST dimension and total scores, [REDACTED], and EQ VAS score) or
- applicable to one UL only (TETRAS Performance subscale dominant UL, TETRAS Performance subscale non-dominant UL).
- *Category B*: endpoints that are determined for both ULs (dominant and non-dominant) separately (i.e., TremorTek® angular tremor amplitude at wrist, elbows, shoulder level for the task with maximum amplitude at cycle baseline and changes thereof from study baseline and Cycle 2).

If not otherwise specified, endpoints in Category B will be summarized by UL (dominant/non-dominant).

4.1.1 Primary Efficacy Endpoint

The primary efficacy endpoint is defined in Section 2.2.1.1.

4.1.1.1 Primary analysis

The primary efficacy endpoint is based on assessments of angular tremor amplitude [deg] for the motor-dominant UL at study baseline⁷ and Week 6 (V4) with standardized computerized kinematic analysis using the TremorTek® device. At each visit, these assessments are performed for four tasks, repeated in three assessments rounds (for further details, please refer to CSP Section 9.1.1.2.1). From these data, the primary efficacy endpoint will be derived as follows:

- The maximum angular tremor amplitude at wrist level will be computed in the following three steps at study baseline (defined at beginning of Section 4):
 1. For each of the four tasks and each of the three assessment rounds, individual 20-second recordings from a kinematic sensor will yield three angular tremor amplitude values in deg for flexion/extension, radial deviation/ulnar deviation and for pronation/supination levels and a single combined Root Mean Square (RMS) angular tremor amplitude value. The RMS will be calculated as (rounded by five decimal places):

$$RMS = \sqrt{\frac{x_1^2 + x_2^2 + x_3^2}{3}},$$
 where
 - x_1 = angular tremor amplitude for flexion/extension [deg]
 - x_2 = angular tremor amplitude for radial deviation/ulnar deviation [deg]
 - x_3 = angular tremor amplitude for pronation/supination [deg]
 2. Calculation of the arithmetic mean from the three assessment rounds of the combined RMS for each of Tasks I to IV [RMS deg], separately for each task (rounded by five decimal places).
 3. Among Tasks I to IV selection of the task with the maximum arithmetic mean calculated during Step 2. The amplitude of this task [RMS deg] will be considered for the primary endpoint.

⁷ For definition of study baseline see beginning of Section 4.

- For the selected task (see Step 3), the angular tremor amplitude at wrist level at Week 6 (V4) [RMS deg] will be derived analogously, i.e., as arithmetic mean of the combined RMS (see Steps 1 and 2 above) based on the respective data from V4.
- Change from study baseline to Week 6 [RMS deg] will be calculated by subtracting the maximum angular tremor amplitude at wrist level at study baseline from the respective value at Week 6 (V4), derived as described above.

Derivation of maximum tremor amplitude at wrist level at study baseline (as defined at beginning of Section 4) according to Steps 1 to 3 (see above) is only meaningful if the three angular tremor amplitude values for flexion/extension, radial deviation/ulnar deviation and for pronation/supination levels are each available for all four tasks from all three assessments rounds. Likewise, maximum tremor amplitude at wrist level at Week 6 (V4) can only be calculated as described above if the three above-mentioned angular tremor amplitude values are each available for the selected task from all three assessment rounds. If any of these study baseline or Week 6 (V4) data are missing, the primary endpoint cannot be derived and will be considered as missing. Under the assumption of missingness at random (MAR), missing values will not be replaced for the primary analysis.

The confirmatory analysis of the primary efficacy endpoint will be based on the FAS-UP (OC) using least square means (LS Means) from a baseline-adjusted analysis of covariance (ANCOVA) as implemented in SAS PROC MIXED. Fixed class effects will be the treatment group (NT 201 versus placebo) and study site. Study baseline angular tremor amplitude at wrist level for the task with the maximum amplitude will be the fixed continuous covariate. Variances will be allowed to differ between treatment groups. Denominator degrees of freedom will be calculated according to the Kenward-Rodger method.

The difference in LS Means between treatment groups with associated 95% CI from this model will serve as an estimate for the size of the treatment effect. The two-sided t-test of the LS Mean treatment difference will be applied to the following testing problem at $\alpha_{2\text{-sided}}=5\%$:

$$H_0: \mu_{NT201} - \mu_{Placebo} = 0 \quad \text{vs.} \quad H_1: \mu_{NT201} - \mu_{Placebo} \neq 0,$$

where $\mu_{NT201} - \mu_{Placebo}$ denotes the expected mean treatment difference on the primary efficacy endpoint, with a negative difference indicating a treatment effect in favor of NT 201.

In case of convergence issues, study sites might be pooled for statistical analysis. Prior to unblinding, no need of pooling was seen for the primary analysis (see also Section 4.7.3).

SAS code similar to the following statements will be used:

```
PROC MIXED data = dataset;
  CLASS TRT01P (REF='C1 Placebo') SITEID;
  MODEL CHG = TRT01P SITEID BASE / solution ddfm=kr;
  LSMEANS TRT01P / pdiff=control('C1 Placebo') CL alpha=0.05;
  REPEATED / group=trt01p;
  WHERE avisit eq 'Week 6 (V4)' and param eq 'Angular tremor amplitude at
  wrist level dominant UL: Task with maximum amplitude at study baseline';
RUN;
```

Here, “TRT01P” denotes the randomized treatment group, “SITEID” the study site, “CHG” the change from study baseline to Week 6 (V4) in maximum tremor amplitude measurement at wrist level [RMS deg] during the unilateral treatment period (i.e., the primary endpoint, derived as described above), and “BASE” maximum tremor amplitude measurement at wrist level at study baseline (derived as described above).

The following statistics will be displayed:

- n (number of values analyzed)
- p-values of fixed class effects and the fixed continuous covariate
- LS Means of each treatment group (including standard error [SE] and 95% CI)
- LS Mean treatment difference (including SE, 95% CI, and t-test p-value).

